6.8.6 HIBM-FAS Total and Mobility Subscale Score vs. 6MWT Distance

GEE will be used to assess the relationship between changes in self-reported functional disability and changes in walking ability (6MWT). Changes in HIBM-FAS total and HIBM-FAS Mobility subscale score will be compared to changes in 6MWT distance. The GEE will be performed with and without treatment in the model for Part II in UX001-CL202. Additional comparisons may be made to explore the changes in these parameters over the dosing pathways identified in [Table 3](#) and in [Table 8](#).

6.8.7 HIBM-FAS Total and Mobility Subscale Score vs. Gait Speed Test

GEE will be used to assess the relationship between changes in self-reported functional disability and changes in comfortable gait speed (CGS) and maximum gait speed (MGS). Changes in HIBM-FAS total and HIBM-FAS Mobility subscale score will be compared to changes in CGS and MGS (as measured in cm/s). The GEE will be performed with and without treatment in the model for Part II in UX001-CL202. Additional comparisons may be made to explore the changes in these parameters over the dosing pathways identified in [Table 3](#) and in [Table 8](#).

6.8.8 HIBM-FAS Total and UE Subscale Score vs. Weighted Arm Lift Test

GEE will be used to assess the relationship between changes in self-reported functional disability and weighted arm lift test. Changes in HIBM-FAS total and HIBM-FAS Mobility subscale score will be compared to changes in weighted arm lift test scores. The GEE will be performed with and without treatment in the model for Part II in UX001-CL202. Additional comparisons may be made to explore the changes in these parameters over the dosing pathways identified in [Table 3](#) and in [Table 8](#).

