6.5.2 Derived Efficacy Variables

Muscle Strength - Hand Held Dynamometry (HHD):

HHD Upper Extremity (UE) composite score is calculated as the sum of the average of the right and left raw scores (as measured in kg) for the following muscle groups: grip, shoulder abductors, elbow flexors and elbow extensors. If a value from the right or left side of an individual muscle group is missing, the missing value will be imputed using the non-missing value from the other side.

HHD Lower Extremity (LE) composite score is calculated as the sum of the average of the right and left raw scores (as measured in kg) for the following muscle groups: hip flexors, hip extensors, hip abductors, hip adductors and knee flexors. Knee extensors will not be included in the calculation of the LE HHD composite score. If a value from the right or left side of an individual muscle group is missing, the missing value will be imputed using the non-missing value from the other side.

Predicted normal HHD values will be derived for the raw strength values from bilateral pinch (tip, key and palmar), grip, shoulder abductors, elbow flexors, elbow extensors, hip flexors, hip extensors, hip abductors, hip adductors, knee flexors and knee extensors collected at baseline using the regression equations generated for the variables. Baseline predicted normal values will be used to derive % of predicted normal values for all future study time points throughout the study.

% of predicted normal HHD values for the individual muscle groups will be calculated as follows: $[(\text{Raw strength value}/\text{Predicted normal strength value}) * 100]$.

Patient Reported Outcomes:

HIBM Functional Activities Scale (HIBM-FAS) Total Score will be calculated as the sum of the Total Scores range from 0 to 100 with higher scores representing greater independence with functional activities. Subscale scores will be calculated for the Mobility, Upper Extremity and Self-Care domains. Mobility subscale scores range from 0 to 40 with higher scores representing greater mobility. Upper Extremity subscale scores range from 0 to 32 with higher scores representing more skilled, independent use of the arms during functional

activity performance. Self-Care subscale scores range from 0 to 28 with higher scores representing greater independence with functional care activities.

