6.8.4 HIBM-FAS Total and UE Subscale Score vs. HHD UE Composite Score

GEE will be used to assess the relationship between changes in self-reported functional disability and changes in upper extremity strength. Changes in HIBM-FAS total and HIBM-FAS UE subscale score will be compared to changes in HHD UE composite score. The GEE will be performed with and without treatment in the model for Part II in UX001-CL202. Additional comparisons may be made to explore the changes in these parameters over the dosing pathways identified in [Table 3](#) and in [Table 8](#).

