506	Serum CK- Treatment Naïve Secondary Analysis- 6MWT >= 200
507	HHD Lower Extremity CS vs. 6MWT Analysis
508	HHD Lower Extremity CS vs. Gait Speed Analysis
509	FAS Total Score and FAS Upper Extremity Score vs. HHD Upper Extremity CS
510	FAS Total Score and FAS Mobility Score vs. HHD Lower Extremity CS
511	FAS Total Score and FAS Mobility Score vs. 6MWT Distance
512	FAS Total Score and FAS Mobility Score vs. Gait Speed Test
513	FAS Total Score and FAS Upper Extremity Score vs. Weighted Arm Lift Test

⁽¹⁾ The final ICH compliant numbering schema will be completed with each delivery of planned analyses and/or final clinical study report. Numbering provided herein may be updated, without update or amendment to the SAP.

⁽²⁾ Supporting Figures will be developed for most tables. The title (and brief description of type of figure) are aligned for reference in development. Figures will assume the name numbering as the primary table.

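### SAP 6.8.8 pairs the HIBM-FAS Mobility subscale with the arm lift test in its body, while its heading, the table of contents and planned Table 513 name the Upper Extremity subscale

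*SAP*

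**What the plan says.** SAP section 6.8 plans a set of GEE analyses relating changes in one efficacy measure to changes in another. The last of them, 6.8.8, is headed "HIBM-FAS Total and UE Subscale Score vs. Weighted Arm Lift Test", and the SAP table of contents lists it under the same title.

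The body opens with a general aim that names no subscale: "GEE will be used to assess the relationship between changes in self-reported functional disability and weighted arm lift test". The next sentence names the scores: "Changes in HIBM-FAS total and HIBM-FAS Mobility subscale score will be compared to changes in weighted arm lift test scores". The section then asks for the model with and without treatment and allows optional further comparisons.

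The list of planned outputs in section 8.1 describes Table 513 as "FAS Total Score and FAS Upper Extremity Score vs. Weighted Arm Lift Test".

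**The concern.** The sentence that names Mobility is the analysis instruction, the one a programmer would code from. It disagrees with the title above it and with the title of the output that it is meant to produce.

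What is at stake is one association: whether change in the arm-function subscale tracks change in an observed arm task. Protocol 7.5.2.5 describes the HIBM-FAS as still under development, and Protocol 7.5.6 gives further validation of the instrument as a reason for using it here. Its agreement with performance tests is therefore of some interest. Within SAP 6.8 the Upper Extremity subscale appears in only two sections: 6.8.4, against strength, and 6.8.8, against a performance test. On a literal reading of 6.8.8 the second of these drops out.

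**Working it through.** No sample size, power or error rate is involved, so the check is a comparison of texts followed by a count.

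**1. The four places that define this analysis**

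| Place in the SAP | HIBM-FAS scores paired with the arm lift test |
|---|---|
| Table of contents, 6.8.8 | Total and Upper Extremity |
| Heading of 6.8.8 | Total and Upper Extremity |
| Body of 6.8.8 | Total and Mobility |
| Section 8.1, Table 513 | Total and Upper Extremity |

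Three say Upper Extremity and one says Mobility. All four agree on the Total score.

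**2. The sibling sections**

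The other upper-limb section that uses the scale, 6.8.4, is consistent between heading and body: "Changes in HIBM-FAS total and HIBM-FAS UE subscale score will be compared to changes in HHD UE composite score". Sections 6.8.5 to 6.8.7 pair Mobility with leg strength, 6MWT distance and gait speed, and each agrees with its own heading. The sentence in 6.8.6 reads "Changes in HIBM-FAS total and HIBM-FAS Mobility subscale score will be compared to changes in 6MWT distance". The sentence in 6.8.8 has the same form with only the last term changed, so a carried-over word is the likely cause. That is an inference from the wording; the SAP does not say so.

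**3. What the scores measure**

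Section 6.5.2 describes the two subscales as follows: "Upper Extremity subscale scores range from 0 to 32 with higher scores representing more skilled, independent use of the arms during functional" activities, and "Mobility subscale scores range from 0 to 40 with higher scores representing greater mobility". Section 6.7.11 describes the arm lift test as overhead lifting of a weight with each arm. The Upper Extremity subscale is the natural counterpart. The SAP gives no reason for pairing Mobility with this test, and section 8.1 lists no table for that pairing. The missing table is supporting evidence only, because the list does not mirror 6.8 exactly: 6.8.1 has no table in the 507 to 513 block either.

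**4. How much is affected**

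Count each combination of one measure with one other as a pairing:

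- 6.8.1 and 6.8.2: 1 each
- 6.8.3: 2 (comfortable and maximum gait speed)
- 6.8.4, 6.8.5 and 6.8.6: 2 each (two HIBM-FAS scores)
- 6.8.7: 2 scores × 2 gait speeds = 4
- 6.8.8: 2

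Total: 1 + 1 + 2 + 2 + 2 + 2 + 4 + 2 = 16.

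The contradiction affects 1 of the 2 pairings in 6.8.8, or 1 of 16 across section 6.8. Each pairing is to be modelled with and without treatment, so a literal reading loses 1 × 2 = 2 model fits and adds two that no listed table would report.

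**5. Is it resolved elsewhere?**

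The last sentence of 6.8.8 permits additional comparisons, but it is optional and refers back to the parameters just named. Sections 6.5 and 8.1 allow extra tables without an SAP amendment, again as an option. None of these says which subscale is meant.

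**The case against.** The strongest reply is that little harm is likely. Three of four places agree, 6.8.4 shows the intended pattern, and a programmer filling a table titled with the Upper Extremity score would meet the mismatch. Section 8.1 also refers to a separate programming specification, which may already have it right. That is fair as to likelihood. But the specification is not available here, and section 8.1 lets mock shells change without an SAP amendment, so the conflict could be settled in programming with no record in the plan. For a document that calls itself an a priori plan (SAP section 1), the variable should be fixed in the text.

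The limits on the consequence also stand. A reader might infer that the question of 6.8.8 as a whole would go untested. The documents do not support that: the stated aim concerns functional disability in general, and the same sentence still specifies the Total score against the arm lift test.

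A reader might also infer that the whole of 6.8.8, one of the eight analyses, rests on a wrong predictor. Only one of its two pairings is affected, and the SAP says that changes are compared without saying which variable is the predictor.

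Finally, it is tempting to call Mobility a lower-limb measure. Section 6.5.2 does not define it that way, and no item content is given. The reading is reasonable from the pairings in 6.8.5 to 6.8.7, but it is an inference.

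**Conclusion.** The contradiction is real and is unresolved in the documents. It is an internal inconsistency in an analysis instruction; nothing suggests a deliberate choice of Mobility. Followed literally, the instruction leaves the Upper Extremity subscale against arm lift comparison unfitted and Table 513 unfillable as titled.

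The importance is low. Section 6.8.8 is a supportive association analysis outside the primary and secondary comparisons of SAP Table 8. The study is not powered for formal comparisons (SAP 6.1), and nothing in the sample size, the efficacy comparisons or the safety analyses depends on this pairing. The loss also arises only if the analyst follows the body over the heading and the table title. That Upper Extremity is the intended subscale rests on the agreement of the other three places and on the subscale descriptions; the sponsor can confirm it.

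**What to change.** In the body sentence of SAP 6.8.8, replace Mobility with Upper Extremity, so that it agrees with the heading, the table of contents and Table 513. If Mobility against arm lift was intended as an additional comparison, keep both subscales in the sentence, say that Mobility is an addition, and add a table for it to section 8.1.

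The first option is a correction to one term. It needs no new data and leaves Table 513 as listed. The second costs one more sentence and one more table. Either way, check that the programming specification for Table 513 matches the corrected text before the analysis is run.

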6.9 Statistical Analysis: Pharmacokinetics

6.9.1 Free Serum Sialic Acid (SA) Levels

Blood samples for the measurement of trough levels of free serum SA will be drawn during blood draws for clinical laboratory samples. Free serum SA samples are being assessed at baseline and the Part I termination visit, and at months 1, 3, 6, 12, 24, 36, and the termination visit in Part II in UX001-CL202 for subjects who roll-over from UX001-CL201. Treatment Naïve subjects who are enrolled in Part II of this study will have a baseline assessed at the screening visit.

Free SA levels in serum assess the drug concentration in the bloodstream resulting from treatment and are the best indicator of compliance with the treatment regimen. Free SA levels in serum are expressed in micrograms of SA per ml of serum. Free serum SA levels observed for the 12g/day SA-ER/SA-IR dose will be evaluated at each study time point using descriptive statistics.

The change in free serum SA level from Baseline to the 6-month Part II time point will be analysed using a GEE model with baseline free serum SA level as a covariate for the 12g/day SA-ER-SA-IR dose group in Part II. Comparisons identified in [Table 8](#) will be implemented for this analysis.

6.10 Statistical Analysis: Safety

In general all safety analyses will be completed using descriptive summaries, graphs, and subject listings. No planned inferential testing of safety endpoints is planned. If after the any planned analysis it is determined by the medical writer and study medical monitor that inferential tests of significance may help to provide context for safety information these tests may be performed and identified in the CSR.

6.10.1 Adverse Events

Adverse Events will be assessed at all visits and throughout the course of the study. The number and percent of subjects with any treatment-emergent adverse events (TEAEs) will be displayed by system organ class and preferred term for each treatment group (6g/day SA-ER, 12g/day SA-ER/SA-IR). Within each preferred term, subjects will be counted only once if they had more than one event reported during the treatment period. The same summary will be performed for all serious TEAEs and all TEAEs causing discontinuation of study drug.

The number and percent of subject TEAEs will also be summarized by greatest reported severity grade (Grades 1-5) for each event preferred term by treatment group. Wherever possible, the severity of all AEs observed will be graded using the NCI CTCAE (V4.0) as follows in [Table 9](#):

Table 9 NCI-CTCAE Common AE Grading Criteria

Grade	Description
1	Mild; asymptomatic or mild symptoms; clinical or diagnostic observations only; intervention not indicated.
2	Moderate; minimal, local or noninvasive intervention indicated; limiting age-appropriate instrumental ADL*.
3	Severe or medically significant but not immediately life-threatening; hospitalization or prolongation of hospitalization indicated; disabling; limiting self-care ADL**.
4	Life-threatening consequences; urgent intervention indicated.
5	Death related to AE.
Source: Common Terminology Criteria for Adverse Events (CTCAE), Version 4.0, Published May 28, 2009 (v4.03, June 24, 2010); USHHS/NIH/NCI * ADL=Activities for Daily Living: Instrumental ADL refer to preparing meals, shopping for groceries or clothes, using the telephone, managing money, etc. ** Self-care ADL refer to bathing, dressing and undressing, feeding self, using the toilet, taking medications, and not bedridden.	

The majority of AEs and TEAEs can be graded using the NCI-CTCAE system. Wherever possible, the severity of all AEs will be graded using the NCI CTCAE. The majority of AEs can be graded using this system. If an AE cannot be graded using the CTCAE criteria, it should be graded as mild, moderate, severe, life-threatening, or death using the definitions in Table 10.

Table 10 Mapped AE Grading Criteria

Grade	Description
Mild (Grade 1)	Awareness of signs or symptoms, but easily tolerated and of a minor irritant type, causing no loss of time from normal activities. Symptoms do not require therapy or a medical evaluation; signs and symptoms are transient.
Moderate (Grade 2):	Events introduce a low level of inconvenience or concern to the participant and may interfere with daily activities, but are usually improved by simple therapeutic measures; moderate experiences may cause some interference with functioning.
Severe (Grade 3)	Events interrupt the participant's normal daily activities and generally require systemic drug therapy or other treatment; they are usually incapacitating.
Life-threatening (Grade 4)	Events that place the participant at immediate risk of death or are disabling.
Death (Grade 5)	Events that result in death

The number and percent of subjects reporting one or more TEAEs that map to the severity grade classification for each preferred term will be summarized by treatment group. At each level of summarization (system organ class or event preferred term) subjects are only counted once.

The number and percent of subjects experiencing Serious Adverse Events (SAE) for each preferred term will be summarized by treatment group.

The number and percent of subjects who withdraw from the study or discontinue study medication due to a TEAE or SAE will be summarized by treatment group.

The number and percent of subject TEAEs will be summarized by greatest reported relationship to study medication in as follows in [Table 11](#).

Table 11 AE Relationship to Study Medication

Relationship	Description
Not-Related	This category applies to an AE that is clearly not related to the investigational agent/procedure, beyond a reasonable doubt. That is, another cause of the event is most plausible; and/or a clinically plausible temporal sequence is inconsistent with the onset of the event and the exposure to study drug and/or a causal relationship is considered biologically implausible.
Possibly-Related	This category applies to an AE that follows a reasonable temporal sequence from administration of the study drug and that follows a known or expected response pattern to the suspected study drug, but that could readily have been produced by a number of other factors.
Probably-Related	This category applies to an AE that is likely related to the investigational agent/procedure. That is, the AE has a temporal relationship to the administration of the investigational agent(s) or research intervention, follows a known or suspected pattern of response, and is strongly associated with study drug exposure.

A listing will be produced for all subjects who reported serious TEAEs or who discontinued study medication due to TEAEs.

All TEAEs will be listed individually by subject. In addition, a separate listing will be produced for AEs that are not treatment-emergent. Separate individual subject listings for SAE and TEAE leading to Study Withdrawal or discontinuation of Study Medication will also be produced.

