7.3.3.1 Stopping Rules

A DMC will be constituted for Study UX001-CL202 and will act in an advisory capacity to Ultragenyx to monitor the safety of SA-ER/SA-IR in subjects who participate in the study (see Section 7.6.3). The DMC may provide advice to Ultragenyx in any determination of whether study enrollment should be paused or if the study should be halted.

AEs will be graded according to the National Cancer Institute Common Terminology Criteria for Adverse Events (NCI CTCAE). If two subjects develop the same unexpected Grade 3 AE that is possibly or probably related to study drug or any subject develops an unexpected Grade 4 AE that is possibly or probably related to study drug, enrollment of new subjects may be suspended until a thorough evaluation can be performed. Should these AEs occur, a full clinical evaluation will be performed by the medical monitor, principal investigators, and DMC in order to make a decision regarding what actions to take, including whether to suspend or resume enrollment, or recommend stopping the study after Institutional Review Board (IRB)/Ethics Committee (EC) review. The recommendations from the medical monitor and investigators will be forwarded to the IRB/EC for review and approval.

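### The two severity scales grade a disabling event differently, and the safety trigger separately leaves out Grade 5

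*SAP*

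**What the plan says.** **Choice of scale.** SAP 6.10.1 uses CTCAE v4.0 wherever possible, with the criteria in Table 9. The fallback is conditional: "If an AE cannot be graded using the CTCAE criteria, it should be graded as mild, moderate, severe, life-threatening, or death"; Table 10 defines those levels. Protocol 8.5.2 has the same two-step rule and the same fallback definitions.

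**Where a disabling event sits.** Table 9, Grade 3, reads "Severe or medically significant but not immediately life-threatening; hospitalization or prolongation of hospitalization indicated; disabling; limiting self-care ADL"; its Grade 4 reads "Life-threatening consequences; urgent intervention indicated". Table 10, Grade 4, labelled life-threatening, reads "Events that place the participant at immediate risk of death or are disabling". Its Grade 3 describes events that "generally require systemic drug therapy or other treatment; they are usually incapacitating".

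**What the grades feed.** SAP 6.10.1 has treatment-emergent AEs (TEAEs) "summarized by greatest reported severity grade (Grades 1-5) for each event preferred term by treatment group". SAP 8.1 lists this as planned Table 13. No split by scale is planned.

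**The trigger.** Protocol 7.3.3.1 says AEs are graded by CTCAE and then names two conditions. One is the same unexpected, related Grade 3 AE in two subjects. The other is that "any subject develops an unexpected Grade 4 AE that is possibly or probably related to study drug". If either occurs, enrollment of new subjects may be suspended, and a full evaluation by the medical monitor, the investigators and the data monitoring committee (DMC) is required.

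**The concern.** A fallback scale is useful only if its grades mean the same as those of the scale it replaces. Table 10 is presented as mapped to Grades 1-5, but for *disabling* it lands one grade higher than Table 9 and under a label that says life was threatened. Readers of the severity table cannot tell which definition produced a given Grade 3 or Grade 4 count.

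This matters somewhat more here than in a trial with fuller safety summaries. SAP 6.10.2 and 6.10.3 plan no descriptive summaries of laboratory or vital-sign data, so the TEAE tables carry most of the quantitative safety reporting. Disabling AEs are plausible in a progressive myopathy in which changes on physical and neurological examination are reported as AEs (SAP 6.10.6 and 6.10.7).

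The trigger in 7.3.3.1 raises two different questions. One is how it treats an event graded only on the fallback scale. The other, unrelated to the scale, is what it does with a death.

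**Working it through.** The documents give no operating characteristics for the trigger and no frequency for fallback-graded events, so there is no figure to reproduce. The check is a comparison of the passages.

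**Step 1: grade one test event on each scale.** Take an event that is disabling but does not immediately threaten life.

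- SAP Table 9: Grade 3, because that row names disabling. Grade 4 is not met, because it needs life-threatening consequences.
- SAP Table 10 and protocol 8.5.2: Grade 4, because disabling is an alternative to immediate risk of death. The Grade 3 row in the same table speaks of usually incapacitating events, which is close in meaning, but only the Grade 4 row names disabling.

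The same event is Grade 3 on one scale and Grade 4 on the other.

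**Step 2: follow it to the output.** Each TEAE enters planned Table 13 with one grade. SAP Table 5 lists both a severity code (AESEV) and a CTCAE grade (AECTCAE), but the SAP does not say how the two are combined for that table. A disabling event graded on the fallback scale therefore appears in the life-threatening row, and a comparable event graded by CTCAE appears in the severe row.

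**Step 3: follow it to the trigger.** Assume the event is also unexpected and possibly or probably related.

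| How the event is graded and read | Subjects needed under 7.3.3.1 |
|---|---|
| Table 9, Grade 3 | 2, with the same AE |
| Fallback Grade 4, fallback grades counted | 1 |
| Fallback Grade 4, only CTCAE grades counted, as 7.3.3.1 cites only CTCAE | none suffices; outside the trigger |

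The second and third rows both differ from the first, so the mismatch does not depend on which reading of 7.3.3.1 is adopted.

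**Step 4: put a death through the trigger.** Death is Grade 5 in Table 9, in Table 10 and in protocol 8.5.2. The Grade 3 condition is not met and the Grade 4 condition is not met. Neither is worded as that grade or higher. The result is the same on both scales, so this gap is independent of Steps 1 to 3.

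**Step 5: size.** The shift is one grade. It applies only to AEs that CTCAE cannot grade. Both documents say the majority can be graded by CTCAE, and neither says how many cannot.

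**The case against.** **A disabling event never reaches Table 10.** Table 9 is generic and already lists disabling under Grade 3, so on this view such an event can always be graded by CTCAE. This does not hold. A generic table that grades everything would leave the stated fallback with nothing to do, yet both documents keep the fallback and claim CTCAE coverage only for the majority of AEs.

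**The trigger cites only CTCAE.** This stands, and it rules out saying flatly that the trigger drops from two subjects to one. It does not remove the mismatch, because exclusion from the trigger also differs from the Table 9 result.

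**Disabling events are captured anyway.** This stands. Significant incapacity is a seriousness criterion (protocol 8.5.1), serious TEAEs have their own table, and all TEAEs are listed by subject. None of this corrects the grade shown in the severity table.

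**Deaths are covered elsewhere.** This stands as a limit on risk. Deaths go to the sponsor within 24 hours (protocol 8.5.4.2), fatal suspected unexpected serious adverse reactions to regulators within 7 calendar days (8.5.4.4), and the DMC may advise a pause or halt. A reader might infer that a related death would go unreviewed; the documents do not support that. What is incomplete is the rule in 7.3.3.1.

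**The consequence is mild.** Suspension is optional and concerns new enrollment, and the protocol synopsis says the additional subjects have already been enrolled. That stands, but the evaluation is mandatory once the trigger is met and can lead to a recommendation to stop the study.

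**Conclusion.** There are two separate wording errors, both minor.

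1. *Disabling* is Grade 3 in SAP Table 9 and Grade 4, labelled life-threatening, in SAP Table 10 and protocol 8.5.2. For the minority of AEs graded on the fallback scale, planned Table 13 can count a disabling event as life-threatening, and 7.3.3.1 treats it differently from the same event graded by CTCAE.
2. Whichever scale is used, 7.3.3.1 stops at Grade 4, so read literally an unexpected, related death does not invoke the evaluation that the section requires.

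The first conclusion assumes that at least one disabling AE cannot be graded by CTCAE. The second rests on the text alone.

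Three stronger inferences are not supported. The severity tables are not unreliable in general, because most AEs are expected to be graded by CTCAE alone. Nothing shows that disabling events will be the commonest severe events or will often meet the trigger: protocol 5.2.3 reports no serious AEs in either dose group at Week 24 of the parent study, and the trigger also requires the event to be unexpected and related, which disease progression would not ordinarily be. Finally, no probability of meeting the trigger can be given, because the documents supply no rate for such events and the answer would be set by whatever rate was assumed.

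**What to change.** - Reconcile SAP Table 9 with SAP Table 10 and protocol 8.5.2 so that *disabling* carries the same grade on both scales.
- Before planned Table 13 is produced, identify any disabling events graded on the fallback scale and apply the reconciled grade.
- Reconcile protocol 7.3.3.1 with the five-grade scale: state which grades it covers, including how a Grade 5 event is handled, and whether grades from the fallback scale count.

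The sponsor, with its clinical and safety reviewers, decides which grade and which trigger apply.

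A flag for the scale behind each grade, or a combined Grade 3-4 row in Table 13, would be optional aids to the reader. Neither repairs the separate Grade 3 and Grade 4 rows or the trigger.

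The cost is wording in the SAP grading tables, in protocol 8.5.2 and in 7.3.3.1. The downside is regrading at most a few events.
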